5.2.2 Secondary Analysis

The same analysis as described for the primary analysis will also be performed for the following:

- Percent change and change from baseline to Week 26 during the placebo-controlled, double-blind treatment period in the combined C5b-9 strata (subjects with elevated C5b-9 blood levels and non-elevated C5b-9 blood levels).
- Percent change and change from Week 26 to Week 52 during the avacopan treatment period in the elevated C5b-9 stratum
- Percent change and change from Week 26 to Week 52 during the avacopan treatment period in the combined C5b-9 strata (subjects with elevated C5b-9 blood levels and non-elevated C5b-9 blood levels).

For percent change and change from Week 26 to Week 52, observed data at Week 26 and Week 52 will be used in the primary analysis and will be conducted in patients who completed Week 26 and Week 52 renal biopsies. The percent change from Week 26 to Week 52 will be only analyzed for subjects for whom the Week 26 activity index score is not 0. Multiple imputation methods similar to the primary endpoint at Week 26 may be explored.

Since the placebo group in Treatment Period A will receive avacopan during the second 26 weeks of the study, the percent change from Week 26 to Week 52 in the C3G Histologic Index for activity in the placebo control group will be compared to the percent change from baseline to Week 26 in the same group. This analysis will be done by the paired t-test. Point estimates and corresponding 95% confidence intervals will be estimated for the difference between the second 26 weeks (avacopan treatment) and the first 26 weeks (placebo treatment). This same analysis will be performed in the avacopan treatment group, comparing percent change from Week 26 to Week 52 in the C3G Histologic Index for activity in the avacopan treatment group to the percent change from baseline to Week 26 in the avacopan treatment group. These analyses will be carried out in the ITT population in the elevated C5b-9 stratum (>244 ng/ml) and separately for the combined C5b-9 strata. These analyses will require non-missing data at Baseline, Week 26 and Week 52. The same analyses will be carried out for change from baseline.

The SAS code to generate the paired t-test will be similar to the following:

The percent change from baseline to Week 52 in the C3G Histologic Index in the avacopan group will also be compared to the percent change from baseline to Week 52 in placebo control group using similar methodology as described for the primary analysis (ANCOVA). Observed data at baseline and Week 52 will used in the analysis. The same analyses will be carried out for change from baseline.

Additional sensitivity analysis may be conducted for the percent change and change from Week 26 to Week 52, by excluding

- Subjects with significant lack of compliance of study medication administration (avacopan /placebo) defined as: All subjects who were <75% compliant overall in Period B.
- Subjects with clinically significant increase in immunosuppressant dose (MMF, Prednisone) or new treatment medications for C3G during Period B

Subjects to be excluded from Period B will be identified and documented prior to the database lock and unblinding for analysis.

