Data from patients who are treatment failures, i.e., requiring treatment rescue measures such as high dose glucocorticoids during the treatment period, will be excluded from efficacy analysis after the point of rescue treatment.

Since the placebo group will receive avacopan during the second 26 weeks of the study, the change from Week 26 to Week 52 in the C3G Histologic Index for activity in the placebo control group will be compared to the change from baseline to Week 26 in this group. This analysis will be done by the paired t-test. Point estimates and corresponding 95% confidence intervals will be estimated for the difference between the second 26 weeks (avacopan treatment) and the first 26 weeks (placebo treatment).

The change from baseline to Week 52 in the C3G Histologic Index in the avacopan group will also be compared to the change from baseline to Week 26 in placebo control group using similar methodology as described for the primary efficacy endpoint.

Continuous variables, including eGFR, UPCR, urinary MCP-1:creatinine ratio, EQ-5D-5L, and SF-36 v2 will be analyzed using a mixed effects model for repeated measures (MMRM) with treatment group, visit, and treatment-by-visit interaction as factors, and baseline as covariate. Patients will be considered as repeated measure units over visits. The interaction term may be dropped if it is not significant at $\alpha = 0.25$ level. Point estimates and corresponding 95% confidence intervals will be estimated for the difference between the avacopan group and the control group at Week 26 using simple contrast from the model.

Similar to the primary endpoint, the second 26 weeks will be compared to the first 26 weeks for the placebo group. Changes in the efficacy parameters across 52 weeks will also be assessed.

Change and percent change in the efficacy parameters during the 8-week follow-up period will also be assessed to determine the off-treatment effect.

Change from baseline in individual components of the C3G Histologic Index activity and chronicity indices as well as glomerular leukocytes and leukocyte subsets based on immunohistochemistry will be summarized and, where appropriate, analyzed using similar methodologies as describe above.

The secondary endpoint of the proportion of patients who have a histologic response will be analyzed by the CMH chi-square test. Data from patients who are treatment failures, i.e., require rescue medication, will be summarized.

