5.2 Primary Efficacy Analysis

The primary efficacy endpoint is the percent change from baseline to Week 26 in the C3G Histologic Index for disease activity. The C3G Histologic Index for disease activity can assume a score from 0-21. See Section 2.3.4 for further details on the calculation of C3G Histologic Index for disease activity.

Statistical Hypothesis Testing and Procedure

• The null hypothesis (H0) is that the avacopan group is not different from the placebo group when comparing the percent change from baseline to Week 26 in the C3G Histologic Index for disease activity.

• The alternative hypothesis (H1) is that the avacopan group is different from the placebo group when comparing the percent change from baseline to Week 26 in the C3G Histologic Index for disease activity.

Numbers, means, median, standard deviation, standard error of means, minimum and maximum will be presented by treatment group and study visit. Avacopan and placebo groups will be compared by Analysis of Covariance (ANCOVA) with treatment group as factor and baseline C3G Histologic Index for disease activity as a covariate. The LS mean estimate and corresponding 95% confidence interval (CI) will be estimated for the treatment main effect. The heterogeneity of the treatment effect across disease diagnoses and renal transplant strata may be investigated through subgroup analyses.

As there are no data available to access the possibility of non-normality distribution of percent change or change from baseline, normality distribution tests will be performed for both percent change and change from baseline. It is possible that the normality test would not hold for percent change from baseline or change from baseline or both. In this case, the following is the analysis procedures for the primary efficacy endpoint.

• If the test for normality fails for percent change from baseline at α level of 0.10 but not change from baseline, change from baseline will be used as the primary endpoint;

• If the test for normality fails for both percent change and change from baseline at α level of 0.10, percent change from baseline will be used as the primary endpoint, but non-parametric methodology will be used for the primary endpoint analysis. The van Elteren's test will be applied to test the percent change from baseline endpoint.

The treatment effect based on the baseline complement profile of subjects may also be investigated.

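### The Week 26 to 52 percent change drops patients whose Week 26 activity score is 0, which tilts the placebo-group paired t-test towards avacopan if any placebo patient reaches 0

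*SAP*

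**What the plan says.** SAP 5.2.2 plans percent change and change from Week 26 to Week 52, on observed biopsies. For percent change there is a restriction: it "will be only analyzed for subjects for whom the Week 26 activity index score is not 0". No such restriction is stated for absolute change.

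The next paragraph of 5.2.2 uses the same variable within the placebo group: "the percent change from Week 26 to Week 52 in the C3G Histologic Index for activity in the placebo control group will be compared" with that group's percent change from baseline to Week 26. "This analysis will be done by the paired t-test", and the estimate is second period (avacopan) minus first period (placebo), so a negative value favours avacopan. Three biopsies are needed: "These analyses will require non-missing data at Baseline, Week 26 and Week 52". The paragraph ends: "The same analyses will be carried out for change from baseline".

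Protocol 8.7.5 words the paired test differently: there "the change from Week 26 to Week 52 in the C3G Histologic Index for activity in the placebo control group will be compared" with the change in the first 26 weeks. A difference in scores needs no rule about zeros. Protocol 8.8 and SAP 9 give this comparison its own power statement, in percent: about 90% power for -35%, with an SD of 34% for each change.

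SAP Section 10 lists the removal of baseline zeros from the ITT population. It lists neither the Week 26 zero rule nor the move of the paired test from change to percent change.

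**The concern.** On the index, "The C3G Histologic Index for disease activity can assume a score from 0-21", so 0 is the floor. In the placebo group the Week 26 score is the outcome of the placebo period. A patient who reaches 0 has the best possible first-period result, -100%, and cannot improve further on avacopan. Such a patient has no second-period percent change, so there is no pair and both values leave the test.

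The exclusion is thus selection on the outcome of one of the two periods being compared. It makes the placebo period look worse and keeps only patients who still had room to improve after the switch. The within-placebo contrast could then suggest a benefit of switching that comes partly from who was left in. SAP 5.2.2 asks for no count of excluded patients and for no sensitivity analysis aimed at this rule; those it lists concern compliance and changes in other treatment.

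**Working it through.** **1. The plan's own figure.** Inputs (Protocol 8.8, SAP 9): n = 22, difference 35, SD 34 for each change, two-sided 0.05. The correlation rho between the two changes is not given. SD of the paired difference = 34 × √(2(1 − rho)). At rho = 0 this is 48.1, and the noncentral t gives power 0.902. The stated figure of about 90% is reproduced.

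**2. Effect of each excluded patient.** Let D be second-period minus first-period percent change, n the placebo patients with three biopsies, k those with a Week 26 score of 0, and D_r the mean among the others. An excluded patient has a first-period change of -100%. The second-period value is undefined, but the score cannot fall below 0, so the value most favourable to avacopan that could be assigned is 0%. Then D for that patient is at least 0 − (−100) = +100.

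- Mean with these patients kept: [(n − k) × D_r + 100k] / n
- Shift from dropping them: D_r minus that mean = k × (D_r − 100) / n

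The shift is negative whenever k ≥ 1 and D_r < 100. With n = 22 and k assumed:

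| k | D_r = 0: mean if kept | shift | D_r = −35: mean if kept | shift |
|---|---|---|---|---|
| 0 | 0 | 0 | −35 | 0 |
| 1 | +4.5 | −4.5 | −28.9 | −6.1 |
| 2 | +9.1 | −9.1 | −22.7 | −12.3 |
| 3 | +13.6 | −13.6 | −16.6 | −18.4 |
| 4 | +18.2 | −18.2 | −10.5 | −24.5 |

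**3. No true change, simulated.** The documents give no mean score, no correlation and no rate of zeros, so all three are assumed. Each patient has a normal true score and three readings with independent error (SD 1.5), rounded and held to 0–21. Baseline zeros are dropped, as in SAP 3.2.2. The implied correlation is 9/(9 + 2.25) = 0.80 for a true-score SD of 3 and 4/(4 + 2.25) = 0.64 for an SD of 2. The true value of D is 0.

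| Mean (SD) | Week 26 zeros | Period 1, all | Period 1, retained | Period 2, retained | D, SAP rule | D, absolute change, zeros kept (score points) | D, both periods divided by baseline |
|---|---|---|---|---|---|---|---|
| 8 (3) | 0.8% | 6.0 | 6.9 | 6.1 | −0.8 | +0.02 | −6.0 |
| 6 (3) | 2.6% | 8.0 | 10.9 | 8.9 | −2.0 | +0.07 | −7.9 |
| 5 (3) | 4.4% | 8.5 | 13.5 | 9.8 | −3.7 | +0.10 | −8.5 |
| 4 (2) | 5.3% | 11.8 | 18.1 | 13.0 | −5.0 | +0.13 | −11.6 |
| 3 (2) | 9.7% | 9.8 | 21.6 | 12.3 | −9.3 | +0.21 | −9.7 |

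The first-period mean over all patients is close to the second-period mean. The gap opens when the zeros are removed and the retained first-period mean rises, so the bias comes almost entirely from the exclusion.

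With the correlation set to 0.6 and means of 4 to 8 (0.5% to 5.6% zeros), the SAP rule gives about −0.6 to −5.5 points, absolute change is off by at most 0.14 score points, and dividing both periods by baseline gives about −9 to −15. At mean 5, for example, the first-period mean is 15.0 over all patients and 20.6 among those retained, and the second-period mean is 15.6: 15.6 − 20.6 = −5.0.

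**4. Loss of pairs.** At rho = 0, power falls from 0.902 (n = 22) to 0.887, 0.870, 0.851 and 0.829 at n = 21, 20, 19 and 18.

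**The case against.** The case for leaving the rule alone has real content.

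- **The event may be rare.** A score of 0 needs all seven lesions at 0, in a patient enrolled with biopsy-proven proliferative disease and then given placebo. The documents give no rate. With no such patient, the rule does nothing. This stands.
- **The bias is modest on the plan's scale.** About −0.6 to −5.5 points compares with a planned −35 and an SD of 34. In no-change simulations at n = 22, false rejection favouring avacopan was 2.7% to 4.3% against a nominal 2.5%, and total two-sided rejection was about 4.3% to 5.5%. This stands: the distortion is mainly one of direction and estimate.
- **Percent change from 0 is undefined**, so this metric needs some rule, and it is better stated in advance. True, but that is a reason not to let this metric lead.
- **Analyses that keep these patients are planned.** The absolute-change version stands beside the percent version, and the baseline-to-Week 52 comparison in SAP 5.2.2 uses baseline as denominator. This is a real mitigation; what remains is which version leads and what is reported.
- **The protocol is not uniform.** Its analysis section specifies change, while its power statement is in percent. So percent change was not foreign to the protocol, but the test as specified there needed no exclusion.
- **Low inferential weight.** This is an uncontrolled before-after comparison outside the ordered testing sequence of SAP 3.1.

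A reader might infer that the between-arm Week 26 to 52 comparison is also biased towards avacopan. The documents do not support that. The selection applies there too, but both arms receive avacopan in that period, and nothing given fixes how many zeros each arm has. Nor does the rule touch the primary comparison, which divides by the baseline score.

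**Conclusion.** The concern holds for the placebo-group paired t-test on percent change. If at least one placebo patient scores 0 at Week 26 and the retained mean difference is below +100 points, the rule shifts the contrast towards avacopan.

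The shift is zero without such patients and about 4.5 to 6 points for each one in 22. Those figures assume retained mean differences of 0 and −35 and an assigned second-period change of 0% for the excluded patient. In smaller paired sets each exclusion weighs more, since the shift is divided by n. The simulated range of about −0.6 to −5.5 points rests on assumed mean scores of 4 to 8, a correlation of 0.6 and no true change.

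It would go too far to conclude that the paired result will be materially wrong, since the rate of zeros is unknown. The point merits a change because a nearly unbiased version of the same test is already in the plan.

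**What to change.** In SAP 5.2.2:

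1. Make absolute change the lead for the paired tests and for the Week 26 to 52 analysis, in line with Protocol 8.7.5, and state that patients with a Week 26 score of 0 are kept.
2. Report percent change from Week 26 descriptively, with the number excluded for a zero score in each arm.
3. List the zero rule, and how the lead measure differs from the protocol, in Section 10.

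Do not repair the percent scale by dividing both periods' changes by baseline. It keeps every patient, but under no change it is biased towards avacopan through regression to the mean, by more than the present rule in every scenario above.

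The cost is SAP wording; the data are the same. One small downside is that the lead result would be in score points, so the paired power statement in Protocol 8.8 and SAP 9, given in percent, would no longer apply to it directly. That should be said there.

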Study medication must be permanently discontinued ([FDA Guidance 2009](#)) if any of the following markers of hepatic injury and/or impaired liver synthetic function are observed, and cannot be attributed to a reversible etiology unrelated to study medication (e.g., cholelithiasis):

- ALT or AST $>8x$ ULN
- ALT or AST $>5x$ ULN for more than 2 weeks
- ALT or AST $>3x$ ULN and (Total Bilirubin $>2x$ ULN or INR >1.5)
- ALT or AST $>3x$ ULN with the appearance of fatigue, nausea, vomiting, right upper quadrant pain or tenderness, fever, rash, and/or eosinophilia ($>5\%$)

If a patient develops Grade 3 or greater leukopenia (WBC count $<2 \times 10^9/L$) or neutropenia ($<1 \times 10^9/L$), or Grade 4 lymphopenia ($<0.2 \times 10^9/L$), then study drug (avacopan or placebo) must be paused in this patient. In addition, if a patient develops Grade 2 leukopenia (WBC count $<3 \times 10^9/L$, but $\geq 2 \times 10^9/L$), the patient must be followed closely for infection and for further significant reduction (reduction by an additional $0.5 \times 10^9/L$ or more, or to $<2 \times 10^9/L$) in WBC count; if either occurs, then study drug must be paused in this patient. Study drug may be resumed only if the abnormal value returns to normal and the Investigator deems resumption to be appropriate.

If a patient develops Grade 3 or worse CPK increase (>5 times the upper limit of normal), dosing with study drug must be paused in this patient. Study drug may be resumed only if the CPK returns to normal levels.

Patients who experience deteriorating renal function based on an increase in serum creatinine of at least 50% (confirmed by a repeat measurement after at least 2 weeks) which is otherwise not explained (e.g., dehydration, new medication), or an increase in proteinuria of >3 g/g creatinine (confirmed by a repeat measurement after at least 2 weeks) from Screening or baseline during the 52-week treatment period, will exit the treatment phase of the study and be treated at the discretion of their physician. The increase of serum creatinine or proteinuria will be calculated from the higher value that is measured either at Screening or baseline. They will remain in the study for follow up and complete the remaining study visits and procedures. If a patient refuses further study participation, the Early Termination visit procedures will be performed, if possible. These patients will be considered treatment failures.

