3.2.3 Safety Population

The Safety Population will include all subjects who are randomized and have received at least one dose of study drug, including all subjects who have not yet completed the Week 26 visit. All

safety data will be analyzed using the Safety Populations according to the actual treatment received.

Notations for Treatment Periods

Treatment Period A: Initial 26-week placebo-controlled, double-blind treatment period, Day 1 – Week 26

Treatment Period B: Week 26-Week 52, the Avacopan treatment period plus 8 Weeks of Followup, Week 26 to End of Study (EOS)

3 Safety Populations for this study:

- 1. The Safety Population in the Treatment Period A is defined as all subjects who received at least one dose of blinded Investigational Drug during Treatment Period A.
- 2. The Safety Population in Treatment Period B is defined as all subjects who received at least one dose of Avacopan during Treatment Period B.
- 3. The All Avacopan Treated Population is defined as all subjects who received at least one dose of Avacopan in the study.

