- Percent change from week 26 to week 28, 32, 38, 44 and 52 by prior treatment group during the Avacopan treatment period in the elevated C5b-9 stratum
- Percent change from week 26 to week 28, 32, 38, 44 and 52 by prior treatment group during the Avacopan treatment period in the combined C5b-9 strata (subjects with elevated C5b-9 blood levels and non-elevated C5b-9 blood levels).

Additionally, percent change from baseline in UPCR across the entire study including visits during the follow-up period (Weeks 54, 57 and Week 60) will be summarized by treatment group. The percent change from baseline to Week 52 in UPCR in the avacopan group will be compared to the percent change from baseline to Week 52 in the placebo control group using similar methodology as described for the primary analysis (ANCOVA) of C3G Histologic Index for disease activity. Missing data will not be imputed. Summary and analyses will be carried out in the ITT population in the elevated C5b-9 stratum (>244 ng/ml) and separately for the combined C5b-9 strata.

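### The Week 26–52 switch analyses call the period avacopan treatment but require no avacopan dose, so placebo patients who left treatment in Period A can be counted as switched

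*SAP*

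**What the plan says.** SAP 5.2.2 plans a paired t-test in the placebo arm and describes the estimate as "the difference between the second 26 weeks (avacopan treatment) and the first 26 weeks (placebo treatment". On population it says: "These analyses will be carried out in the ITT population in the elevated C5b-9 stratum", with the combined strata analysed separately. The further entry conditions are non-missing biopsies at Baseline, Week 26 and Week 52 and, for percent change, a Week 26 score other than zero. SAP 3.2.2 admits to ITT a patient with one dose of study medication, which may be placebo.

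Protocol 4.4 says that patients with confirmed renal deterioration "will exit the treatment phase of the study and be treated at the discretion of their physician". It continues: "They will remain in the study for follow up and complete the remaining study visits and procedures". Other patients who stop study drug are also to be followed at scheduled visits for efficacy. The Week 52 biopsy is a scheduled procedure, optional only for adolescents (Protocol 6.19).

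A population that does require Period B avacopan already exists in SAP 3.2.3: "The Safety Population in Treatment Period B is defined as all subjects who received at least one dose of Avacopan during Treatment Period B". It is used only for safety.

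For the later period SAP 5.2.2 offers: "Additional sensitivity analysis may be conducted for the percent change and change from Week 26 to Week 52, by excluding" patients below 75% compliance in Period B, or those with new or clinically significantly increased treatment during Period B. SAP 5.2.3 says that modified multiple imputation may be explored for the same period. SAP 5.3.1.2 analyses UPCR from Week 26 "by prior treatment group during the Avacopan treatment period in the elevated C5b-9 stratum" and in the combined strata; eGFR and other endpoints refer back to it.

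Protocol 8.7.5 excludes data of treatment failures from efficacy analysis after rescue. SAP 5.2.2 does not repeat this rule, and SAP 10 does not list it as changed.

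**The concern.** The paired test is the trial's within-patient look at switching from placebo to avacopan, and it has its own power statement (Protocol 8.8, SAP 9). A placebo patient who exits in Period A and returns for the biopsies supplies a second-period value under the avacopan label without having taken the drug. What that value reflects is the disease course, the physician's chosen therapy, or both.

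Patients who exit for renal deterioration are selected on creatinine or proteinuria and are then likely to be treated, so their change may differ systematically from that of patients who really switched. A reader of the study report would take the estimate as the effect of starting avacopan. No rule that the SAP commits to takes these patients out.

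**Working it through.** **1. Can such a patient enter the test?**

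| Step | Source | Result for a placebo patient who exits in Period A |
|---|---|---|
| ITT: one dose of study medication, baseline activity score not 0, not still awaiting Week 26 | SAP 3.2.2 | met with a placebo dose |
| Leaves treatment phase, stays for visits and procedures | Protocol 4.4 | no Period B avacopan; Week 26 and Week 52 biopsies still due |
| Three biopsies present | SAP 5.2.2 | can be met |
| At least one Period B avacopan dose | SAP 3.2.3, safety only | not applied |
| Below 75% compliance in Period B | SAP 5.2.2, optional | catches the patient if zero capsules count as 0%; written for the Week 26–52 change and does not name the paired test |
| New or increased treatment in Period B | SAP 5.2.2, optional | misses therapy started in Period A and continued |

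**2. The plan's own power figure.** Inputs from SAP 9: n = 22, difference -35, SD 34 for each change, two-sided α = 0.05. The documents give no correlation between the two changes; I assume zero.

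SD of the paired difference = 34 × √2 = 48.1. Noncentrality = 35 / (48.1 / √22) = 3.41 with 21 degrees of freedom. Power = 90.2%, which agrees with the stated figure of approximately 90%.

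**3. Size and direction of the bias.** Let k of the 22 pairs come from patients who never switched. Neither k nor their changes are in the documents; k = 1 to 4 and the patterns below are assumptions. If each such patient's second-minus-first difference is shifted by e and the true switch effect is zero, the mean difference is k × e / 22. Example: k = 4 and e = -100 give 4 × (-100) / 22 = -18.2.

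Rejection rates are from simulated paired t-tests (n = 22, SD 34 per change, independent changes, no true effect), counting only significance in avacopan's favour, nominally 2.5%.

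| Assumed mean change in never-switched patients, Period A / Period B | e | Mean difference, k = 1, 2, 3, 4 | Favouring avacopan, k = 1, 2, 3, 4 |
|---|---|---|---|
| +50 / -50 (worsens, then rescue works after Week 26) | -100 | -4.5, -9.1, -13.6, -18.2 | 4.3, 7.5, 12.8, 20% |
| +35 / -35 (as above, smaller) | -70 | -3.2, -6.4, -9.5, -12.7 | 4.1, 6.4, 9.8, 14.3% |
| 0 / -35 (rescue works after Week 26 only) | -35 | -1.6, -3.2, -4.8, -6.4 | 3.2, 4.3, 5.8, 7.6% |
| -20 / 0 (rescue works before Week 26) | +20 | +0.9, +1.8, +2.7, +3.6 | 2.0, 1.6, 1.3, 1.0% |

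**4. Dilution.** Suppose the true switch effect is -35 and never-switched patients show no difference. The mean is -35 × (22 - k) / 22, which gives -33.4, -31.8 and -28.6 for k = 1, 2 and 4. Power falls to 86.8%, 83.0% and 73.3%.

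**5. Cost of restricting to switched patients.** The formula of step 2 with 22 - k pairs gives 88.7% (21 pairs), 87.0% (20) and 82.9% (18).

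**The case against.** A reader might infer that the test is tilted towards avacopan. The documents do not support that. A patient who exits in Period A may start physician-chosen therapy before the Week 26 biopsy, so part or all of the benefit can fall in the placebo half; SAP 5.2.3 itself anticipates new treatment before that biopsy. The worsen-then-improve pattern fits mainly exits close to Week 26. Exit is triggered by creatinine or proteinuria, not histology, so no histologic swing of 35% or 50% is documented. Patients stopped for liver, blood count or CPK findings are not selected for worsening C3G. All this stands: the direction is open.

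A reader might also infer that UPCR and eGFR are biased to a similar degree. That has not been shown. Those analyses are by prior treatment group, and patients without Period B avacopan can occur in both arms. The labelling gap is the same, but its effect was not quantified.

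Next, Protocol 8.7.5 would remove rescued patients' later data. If it still applies, much of the problem goes, although patients who stopped without rescue remain. SAP 1 says that the SAP's methods supersede the protocol's, and SAP 5.2.2 is silent, so whether the rule survives is unclear. That calls for reconciliation and does not close the gap.

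The optional analyses in SAP 5.2.2 and 5.2.3 do address these patients in part, and exclusions are to be documented before unblinding, but the analyses themselves are not committed. The per-protocol commitment in SAP 5.2.6 covers only the primary analysis.

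Finally, a treatment-policy contrast is legitimate, and requiring a Period B dose conditions on an event after randomisation that is related to the first-period outcome: it removes placebo patients who deteriorated. This is a real cost and the reason to keep the ITT version as a sensitivity analysis. It does not justify the avacopan label on patients who took none. In a before/after contrast within one arm, ITT does not protect a randomised comparison.

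**Conclusion.** The point holds on the text. The paired comparison, and the Week 26–52 analyses described as avacopan treatment, admit placebo patients who never took avacopan, and no committed rule excludes them. The effect is a mislabelled contrast whose bias can go towards avacopan, against it, or towards dilution.

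Under the assumptions shown, the bias is small with one such patient and can be material with four. The documents do not say that any such patient exists, so these figures are a range, not an estimate for this trial.

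The consequence is limited: the paired test is secondary, lies outside the gatekeeping procedure of SAP 3.1, and leaves the primary Week 26 test untouched. The change is still worth making, because the wording is wrong as it stands and the correction is cheap.

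**What to change.** - In SAP 5.2.2, run the first-versus-second-period paired tests and the Week 26–52 change analyses in ITT patients with at least one avacopan dose in Treatment Period B, using the flag defined in 3.2.3. Do the same in 5.3.1.2 and the sections that refer to it.
- Keep the ITT version as a sensitivity analysis, and list never-switched patients with their Period B therapy.
- Change the Period B exclusion analysis from *may* to *will*, apply it to the paired test as well, and include C3G treatment started in Period A and continued into Period B.
- Reconcile Protocol 8.7.5 with the SAP: state whether the exclusion of post-rescue data applies to these analyses and, if it was dropped, list that in SAP 10.

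The cost is SAP wording and one existing flag, a few fewer pairs (power at -35% about 87% with 20 pairs and 83% with 18, against 90% with 22), and selection of patients who stayed on treatment to Week 26, which the retained ITT version makes visible.
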